6.1.2. Study Period

Table AMAG.6.2 defines the study periods.

Table AMAG.6.2. Study Periods

Period	Start Date	End Date
Study Baseline	Informed Consent date	Prior to Visit 2 dose date/time. If dose date is missing, the last date at Visit 2 will be used.
Period 1 (Weeks 0-12)	After Study Baseline end date.	Prior to Visit 8 dose date/time or the date of the ETV (if it occurs between Visits 2 and 8). If dose date is missing, the last date at Visit 8 will be used.
Period 2 (Weeks 12-52)	After Period 1 end date.	Prior to Visit 18 dose date/time or the date of the ETV (if it occurs between Visits 8 and 18). If dose date is missing, the last date at Visit 18 will be used.
Period 3 (Weeks 52-104)	Only for subjects with Clinical Benefit: After Period 2 end date.	Visit 31 dose date or the date of the ETV (if it occurs between Visits 18 and 31). If dose date is missing, the last date at Visit 31 will be used.
Follow-up (Weeks 104-120)	
 • Subjects completed treatment and Period 3: After Period 3 end date. • Subjects discontinued treatment in Period 2 but completed Period 2: After Period 2 end date. • Subjects with no Clinical Benefit and did not enter Period 3: After Period 2 end date. • Subjects discontinued treatment in Period 3 but completed Period 3: After Period 3 end date. 	Visit 804 dose date or the date of the ETV (if it occurs between Visits 801 and 804), whichever is earliest.

Abbreviation: ETV = early termination visit.

6.1.3. Baseline and Postbaseline for Efficacy and Health Outcomes Analyses

Table AMAG.6.3 describes the baseline and postbaseline definitions for efficacy and health outcomes analyses.

Table AMAG.6.3. Baseline and Postbaseline Definitions for Efficacy and Health Outcomes Analyses

Efficacy Analysis Population	Analysis Type	Baseline (Periods as defined in Table AMAG.6.2)	Postbaseline (Periods as defined in Table AMAG.6.2)
ITT, mITT, EHO Group 2, EHO Group 3.	All efficacy and health outcomes analysis.	Baseline is the last non-missing (scheduled or unscheduled) assessment during the Study Baseline period. If time is not collected for a measurement taken on Visit 2 dose date, it will be assumed that it occurred prior to first dose.	Postbaseline: starts at Period 1 start date and ends at the Period end date for the analysis period(s) of interest.

Abbreviations: EHO = efficacy and health outcomes; ITT = intent to treat;

6.1.4. Baseline and Postbaseline for Safety Analyses

Table AMAG.6.4 describes the baseline and postbaseline definitions for safety analyses. Note that an alternative baseline definition may be considered after the IA #1 DBL (example, for Safety Population Period 2, the screening period will be used as the baseline for subjects receiving LY in Period 1; for subjects first receiving LY in Period 2 [i.e., PBO subjects in Period 1], the baseline period will be the time interval [equal in length to screening] leading up to LY administration).

Table AMAG.6.4. Baseline and Postbaseline Definitions for Safety Analyses

Safety Group	Analysis Type	Baseline (Periods as defined in Table AMAG.6.2)	Postbaseline (Periods as defined in Table AMAG.6.2)
Safety Population Period 1 [Weeks 0-12 (Placebo-Controlled)]	1.1) Treatment-Emergent Adverse Events	The baseline period is defined as the Study Baseline period. If time is not collected for an event starting on Visit 2 dose date, it will be assumed that it occurred after first dose.	Period 1 (Weeks 0-12): starts at Period 1 start date and ends at Period 1 end date or the day of the study treatment disposition visit (whichever is earliest) unless otherwise noted.
	1.2) Treatment-Emergent Abnormal Labs and Vital Signs	All scheduled and unscheduled measurements recorded during the baseline period as defined above (1.1). If time is not collected for a measurement taken on Visit 2 dose date, it will be assumed that it occurred prior to first dose.	Period 1 will be defined as above (1.1). All scheduled and unscheduled measurements will be included.
	1.3) Change from Last Baseline to Week xx and to Last Postbaseline for Labs and Vital Signs	The last scheduled non-missing assessment recorded during the baseline period defined above (1.1). If time is not collected for a measurement taken on Visit 2 dose date, it will be assumed that it occurred prior to first dose.	Period 1 as defined above (1.1). Only scheduled visits will be included. The ETVs are considered scheduled visits.

Baseline and Postbaseline Definitions for Safety Analyses

Safety Group	Analysis Type	Baseline (Periods as defined in Table AMAG.6.2)	Postbaseline (Periods as defined in Table AMAG.6.2)
Safety Population Period 2 [Weeks 12-52]	2.1) Treatment-Emergent Adverse Events	An event ongoing at the time of the first dose of Period 2 study treatment. If time is not collected for an event starting on Visit 8 dose date, it will be assumed that it occurred after first dose.	Period 2 (Weeks 12-52): starts at Period 2 Start Date and ends at Period 2 End Date or the day of the study treatment disposition visit (whichever is earliest) unless otherwise noted.
	2.2) Treatment-Emergent Abnormal Labs and Vital Signs	The last non-missing assessment (scheduled or unscheduled) recorded prior to the first dose of Period 2 study treatment. If time is not collected for a measurement taken on Visit 8 dose date, it will be assumed that it occurred prior to first dose.	Period 2 will be defined as above (2.1). All scheduled and unscheduled measurements will be included.
	2.3) Change from Last Baseline to Week xx and to Last Postbaseline for Labs and Vital Signs	The last non-missing scheduled assessment recorded prior to the first dose of Period 2 study treatment. If time is not collected for a measurement taken on Visit 8 dose date, it will be assumed that it occurred prior to first dose.	Period 2 will be defined as above (2.1). Only scheduled visits will be included. The ETVs are considered scheduled visits.
Safety population All SC LY [All treatment periods where LY SC is administered]	3.1) Treatment-Emergent Adverse Events	An ongoing event at the time of the first dose of LY SC treatment. If time is not collected for an event starting on the first dose date, it will be assumed that it occurred after first dose.	LY SC Treatment Period: starts at the administration of the first dose of LY SC treatment and ends at the study treatment disposition visit (ie, the last visit at which the LY SC treatment was administered).
	3.2) Treatment-Emergent Abnormal Labs and Vital Signs	The last non-missing assessment (scheduled or unscheduled) recorded prior to the first dose of LY SC treatment. If time is not collected for a measurement taken on first dose date, it will be assumed that it occurred prior to first dose.	LY SC Treatment Period will be defined as above (3.1). All scheduled and unscheduled measurements will be included.
	3.3) Change from Last Baseline to Week xx and to Last Postbaseline for Labs and Vital Signs	The last non-missing scheduled assessment recorded prior to the first dose of LY SC. If time is not collected for a measurement taken on first dose date, it will be assumed that it occurred prior to first dose.	LY SC Treatment Period will be defined as above (3.1). Only scheduled visits will be included. The ETVs are considered scheduled visits.

Baseline and Postbaseline Definitions for Safety Analyses

Safety Group	Analysis Type	Baseline (Periods as defined in Table AMAG.6.2)	Postbaseline (Periods as defined in Table AMAG.6.2)
Safety Population All LY (a) [All treatment periods where LY (IV or SC) is administered]	4a.1) Treatment-Emergent Adverse Events	
Randomized to LY at Period 1: The baseline period is defined as the Study Baseline period. If time is not collected for an event starting on Visit 2 dose date, it will be assumed that it occurred after first dose.
 
Randomized to Placebo at Period 1: An ongoing event at the time of the first dose of Period 2 study treatment of LY. If time is not collected for an event starting on Visit 8 dose date, it will be assumed that it occurred after first dose.
	
Randomized to LY at Period 1: LY Treatment Period: starts at Period 1 Start Date and ends at the study treatment disposition visit (ie, the last visit at which the LY treatment was administered).
 
Randomized to Placebo at Period 1: LY Treatment Period: starts at the administration of the first dose of Period 2 study treatment of LY and ends at the study treatment disposition visit (ie, the last visit at which the LY treatment was administered).

	4a.2) Treatment-Emergent Abnormal Labs and Vital Signs	
Randomized to LY at Period 1: Baseline will be all scheduled and unscheduled measurements recorded during the baseline period as defined above (4a.1). If time is not collected for a measurement taken on Visit 2 dose date, it will be assumed that it occurred prior to first dose.
 
Randomized to Placebo at Period 1: The last non-missing assessment (scheduled or unscheduled) recorded prior to the first dose of Period 2 LY study treatment. If time is not collected for a measurement taken on Visit 8 dose date, it will be assumed that it occurred prior to first dose.
	
Randomized to LY at Period 1: LY Treatment Period will be defined as above (4a.1). All scheduled and unscheduled measurements will be included.
 
Randomized to Placebo at Period 1: LY Treatment Period will be defined as above (4a.1). All scheduled and unscheduled measurements will be included.

Baseline and Postbaseline Definitions for Safety Analyses

Safety Group	Analysis Type	Baseline (Periods as defined in Table AMAG.6.2)	Postbaseline (Periods as defined in Table AMAG.6.2)
	4a.3) Change from Last Baseline to Week xx and to Last Postbaseline for Labs and Vital Signs	
Randomized to LY at Period 1: The last scheduled non-missing assessment recorded prior to the date of first dose of study treatment during the baseline period defined above (4a.1). If time is not collected for a measurement taken on Visit 2 dose date, it will be assumed that it occurred prior to first dose.
 
Randomized to Placebo at Period 1: The last non-missing scheduled assessment recorded prior to the first dose of Period 2 study treatment. If time is not collected for a measurement taken on Visit 8 dose date, it will be assumed that it occurred prior to first dose.
	
Randomized to LY at Period 1: LY Treatment Period will be defined as above (4a.1). Only scheduled measurements will be included. The ETVs are considered scheduled visits.
 
Randomized to Placebo at Period 1: LY Treatment Period will be defined as above (4a.1). Only scheduled measurements will be included. The ETVs are considered scheduled visits.

Safety Population All LY (b) [All treatment periods where LY (IV or SC) is administered and Follow-Up]	4b.1) Treatment-Emergent Adverse Events	
Randomized to LY at Period 1: The baseline period is defined as the Study Baseline period. If time is not collected for an event starting on Visit 2 dose date, it will be assumed that it occurred after first dose.
 
Randomized to Placebo at Period 1: An ongoing event at the time of the first dose of Period 2 study treatment of LY. If time is not collected for an event starting on Visit 8 dose date, it will be assumed that it occurred after first dose.
	
Randomized to LY at Period 1: LY Treatment Period: starts at Period 1 Start Date and ends at Week 120 (Visit 804). Note that this will include the period after discontinuing treatment.
 
Randomized to Placebo at Period 1: LY Treatment Period: starts at the administration of the first dose of Period 2 study treatment of LY and ends at Week 120 (Visit 804). Note that this will include the period after discontinuing treatment.

Baseline and Postbaseline Definitions for Safety Analyses

Safety Group	Analysis Type	Baseline (Periods as defined in Table AMAG.6.2)	Postbaseline (Periods as defined in Table AMAG.6.2)
	4b.2) Treatment-Emergent Abnormal Labs and Vital Signs	
Randomized to LY at Period 1: Baseline will be all scheduled and unscheduled measurements recorded during the baseline period as defined above (4b.1). If time is not collected for a measurement taken on Visit 2 dose date, it will be assumed that it occurred prior to first dose.
 
Randomized to Placebo at Period 1: The last non-missing assessment (scheduled or unscheduled) recorded prior to the first dose of Period 2 LY study treatment. If time is not collected for a measurement taken on Visit 8 dose date, it will be assumed that it occurred prior to first dose.
	
Randomized to LY at Period 1: LY Treatment Period will be defined as above (4b.1). All scheduled and unscheduled measurements will be included.
 
Randomized to Placebo at Period 1: LY Treatment Period will be defined as above (4b.1). All scheduled and unscheduled measurements will be included.

	4b.3) Change from Last Baseline to Week xx and to Last Postbaseline for Labs and Vital Signs	
Randomized to LY at Period 1: The last scheduled non-missing assessment recorded prior to the date of first dose of study treatment during the baseline period defined above (4b.1). If time is not collected for a measurement taken on Visit 2 dose date, it will be assumed that it occurred prior to first dose.
 
Randomized to Placebo at Period 1: The last non-missing scheduled assessment recorded prior to the first dose of Period 2 study treatment. If time is not collected for a measurement taken on Visit 8 dose date, it will be assumed that it occurred prior to first dose.
	
Randomized to LY at Period 1: LY Treatment Period will be defined as above (4b.1). Only scheduled measurements will be included. The ETVs are considered scheduled visits.
 
Randomized to Placebo at Period 1: LY Treatment Period will be defined as above (4b.1). Only scheduled measurements will be included. The ETVs are considered scheduled visits.

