8.1. Discontinuation from Study Treatment

8.1.1. *Permanent Discontinuation from Study Treatment*

Discontinuation of the investigational product for abnormal liver tests should be considered by the investigator when a subject meets one of the following conditions after consultation with the Lilly designated medical monitor:

- ALT or AST >8xULN
- ALT or AST >5xULN for more than 2 weeks
- ALT or AST >3xULN and TBL >2xULN or prothrombin time >1.5xULN
- ALT or AST >3xULN with the appearance of fatigue, nausea, vomiting, right upper-quadrant pain or tenderness, fever, rash, and/or eosinophilia (>5%)
- ALP >3xULN
- ALP >2.5xULN and TBL >2xULN
- ALP >2.5xULN with the appearance of fatigue, nausea, vomiting, right quadrant pain or tenderness, fever, rash, and/or eosinophilia (>5%).

Subjects may discontinue treatment for any of the reasons noted above, or for other reasons such as the development of a serious adverse event. To better communicate patient flow throughout the study, different study period situations are provided below:

- Subjects who discontinue the investigational product in Period 1 or Period 2 may continue in the study according to the visit schedule (Section 2).
- At Week 52/Visit 18, subjects who have previously discontinued the investigational product will continue to Visit 801 of the Follow-up Period.
- Subjects who discontinue the investigational product in Period 3 may continue in Period 3 and then proceed to Week 104/Visit 801 of the Follow-up Period.

Investigational product is to be discontinued for patients who experience clinically significant systemic hypersensitivity events (such as anaphylaxis) following administration of investigational product.

8.1.2. *Discontinuation of Inadvertently Enrolled Subjects*

If the sponsor or investigator identify a subject who did not meet enrollment criteria and was inadvertently enrolled, a discussion must occur between the sponsor CRP and the investigator to determine if the subject may continue in the study. If both agree it is medically appropriate to continue, the investigator must obtain documented approval from the sponsor CRP to allow the inadvertently enrolled subject to continue in the study with or without treatment with investigational product.

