6.14.2.3. Deaths, Other Serious Adverse Events, and Other Significant Adverse Events

A listing of all deaths will be provided.

The number and percentage of subjects who experienced an SAE (including deaths) during the treatment period will be summarized by treatment using MedDRA PT nested within SOC. Events will be ordered by decreasing frequency in the total LY treatment group within SOC. The summaries will be presented for Safety Population Period 1, Safety Population Period 2, Safety Population All SC LY, and Safety Population All LY.

The number and percentage of subjects who permanently discontinued from study treatment due to an AE (including AEs that led to death) during the treatment period will be summarized by treatment using MedDRA PT nested within SOC. Events will be ordered by decreasing frequency in the total LY treatment group within SOC. The summaries will be presented for Safety Population Period 1, Safety Population Period 2, Safety Population All SC LY, and Safety Population All LY.

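### SAP Table AMAG.6.4 closes the Period 1 and 2 AE windows at an undefined disposition visit; on the SAP's only stated meaning, a between-dose event that ends treatment misses the Period 1 LY versus placebo comparison

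*SAP*

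**What the plan says.** SAP 6.1.4, Table AMAG.6.4, sets the windows for treatment-emergent events.

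- Row 1.1 (Safety Population Period 1): the window "ends at Period 1 end date or the day of the study treatment disposition visit (whichever is earliest) unless otherwise noted".
- Row 2.1 (Safety Population Period 2): it "ends at Period 2 End Date or the day of the study treatment disposition visit (whichever is earliest) unless otherwise noted".
- Row 3.1 (All SC LY) adds an explanation of the term: the window "ends at the study treatment disposition visit (ie, the last visit at which the LY SC treatment was administered").
- Row 4a.1 (All LY, treatment periods only) does the same: it "ends at the study treatment disposition visit (ie, the last visit at which the LY treatment was administered").
- Row 4b.1 (All LY with follow-up) runs to Week 120: "Note that this will include the period after discontinuing treatment".

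Rows 1.1 and 2.1 carry no explanation, and the SAP defines the term nowhere else. Rows 1.2, 1.3, 2.2 and 2.3 apply the same windows to laboratory values and vital signs. SAP 6.14.1 takes exposure as the Table AMAG.6.4 period plus 1 day, and SAP 6.14.2.1 assigns TEAEs to periods by the same table. SAP 6.14.2.3 limits the SAE table to the treatment period. It says of AE discontinuations that subjects who "permanently discontinued from study treatment due to an AE (including AEs that led to death) during the treatment period will be summarized".

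Protocol 8.1.1 keeps early stoppers under observation: "Subjects who discontinue the investigational product in Period 1 or Period 2 may continue in the study according to the visit schedule".

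**The concern.** Period 1 is the only placebo-controlled part of the trial and the only safety set with a planned test, Fisher's exact test of the combined LY arms against placebo (SAP 6.14). AEs and discontinuation rates are the endpoint of a secondary objective. A programmer who looks up the disposition visit finds one meaning in the SAP, the last LY dosing visit. Dosing is every 4 weeks, so a stop decided between doses comes after that visit, and an event that began between doses does too. The comparison could then omit some of the events that were serious enough to end treatment. The omission would be larger in whichever arm had more of them.

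**Working it through.** The plan states no figure on this point, so there is none to reproduce. The check compares the two possible meanings and then does day arithmetic.

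**Inputs**
- Period 1 dosing at Weeks 0, 4 and 8, nominal Days 1, 29 and 57; the next dosing visit is V8, Days 86 to 92 (Protocol Section 2).
- 180 subjects allocated 2:1:1:2 (Protocol 10.1): 180 × 2/6 = 60 on 1000 mg, 180 × 1/6 = 30 on each of 600 mg and 200 mg, and 60 on placebo. Pooled LY = 60 + 30 + 30 = 120, against 60.

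**Reading A: disposition visit = last dosing visit (rows 3.1 and 4a.1 carried into row 1.1)**

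The window of an early stopper closes on the last dosing day. Days lost before the next planned dose = next dosing day − last dosing day − 1, with V8 at its earliest:
- last dose Day 1: 29 − 1 − 1 = 27 days;
- last dose Day 29: 57 − 29 − 1 = 27 days;
- last dose Day 57: 86 − 57 − 1 = 28 days.

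Counted to Day 85, the day before the earliest V8, the loss is 85 − 1 = 84, 85 − 29 = 56 or 85 − 57 = 28 days. A one-dose subject has a window of 0 to 1 day, so exposure under 6.14.1 is about 1 to 2 days.

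**Reading B: disposition visit = visit at which the stop is recorded**

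The event that led to the stop began before that visit, so it is inside the window and counted.

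**What the difference could do to the Period 1 comparison**

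The documents give no expected rate of AE discontinuation. The counts below are assumptions: subjects with a stop-causing event that starts between doses. The p-values are two-sided Fisher's exact.

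| LY (of 120) | Placebo (of 60) | Reading B | Reading A |
|---|---|---|---|
| 6 (5.0%) | 1 (1.7%) | p = 0.43 | 0 vs 0 |
| 8 (6.7%) | 0 (0%) | p = 0.053 | 0 vs 0 |
| 12 (10.0%) | 1 (1.7%) | p = 0.063 | 0 vs 0 |

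With equal rates, such as 6 of 120 and 3 of 60 (5% each), Reading A hides events but creates no difference between the arms.

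**Consistency with the rest of the SAP**

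SAP 6.14.8.3 defines non-immediate hypersensitivity as TEAEs after the day of administration and before the next one. Under Reading A that interval is empty after an early stopper's final dose. Protocol 5.5 projects mean troughs of 2.7 to 13 µg/ml under dosing every 4 weeks, so drug is still expected to be present between doses. Reading A therefore fits poorly with the rest of the plan, but the text does not exclude it.

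**The case against.** The strongest reply is that Reading A was not intended. The explanation is missing from rows 1.1 and 2.1. It names LY, so it cannot apply literally to placebo subjects in Period 1. It would also leave a one-dose subject with almost no exposure. This stands, and it makes the loss in Periods 1 and 2 conditional. It does not remove the problem, because no other meaning is written down. In rows 3.1 and 4a.1 the last-dosing-visit rule is explicit.

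Several stronger conclusions are tempting and are not supported.

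- **That about 96% of stop-causing events are lost.** The figure is 27/28 and needs Reading A, onset spread evenly over the 28 days after the final dose, and no event that began earlier. Protocol 7.8.2.2 requires a permanent stop for systemic reactions during or within 6 hours of an infusion. Those mostly fall on the dosing day and are kept. An event that began before the last dose is also kept.
- **That AE discontinuations disappear by arm.** SAP 6.6 summarises reasons for stopping study drug by treatment group for Period 1 on the ITT population, without the Table AMAG.6.4 window. The overview table in 6.14.2.1 does not repeat the treatment-period limit. In 6.14.2.3 the time phrase can be attached to the discontinuation instead of the event, although under Reading A the stop itself usually follows the last dosing day as well.
- **That serious events vanish.** All deaths are listed (6.14.2.3). Registry SAEs are tabulated by treatment group whether or not they are TEAEs (6.20). Row 4b.1 counts later events for LY-exposed subjects, though in one pooled column.
- **That Period 2 placebo comparisons are affected.** Period 1 placebo subjects receive LY in Period 2, and Table AMAG.6.5 lists no Period 2 comparison.
- **That Reading B is also a defect because later events are cut.** A subject who stops at Week 4 would contribute 4 of 12 weeks. That is an on-treatment choice, and SAP 6.14 allows exposure-adjusted rates if dropout differs between arms.

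**Conclusion.** The point holds in conditional form. One term governs the safety windows, is left undefined in rows 1.1 and 2.1, and is explained in rows 3.1 and 4a.1 in a way that gives a wrong count if carried over. Under that meaning, a between-dose event that ends treatment is missing from the Period 1 TEAE tables and the LY versus placebo comparison. It may also be missing from the SAE and AE-discontinuation tables. Exposure, laboratory values and vital signs are cut at the same day. Under the recorded-stop meaning, the causal event is kept.

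Only subjects who stop early are affected in Periods 1 and 2; for those who continue, the period end comes first. The number of events cannot be derived from the documents, and the counts in the table above are assumed. What would be lost entirely from the AE summary tables under Reading A is narrow: the term-level record of non-serious events in placebo subjects who stopped in Period 1. For LY subjects, the randomised comparison of such events would be lost. This should be corrected because Period 1 is the only randomised safety contrast and the data are already collected.

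**What to change.** 1. Define the study treatment disposition visit once, for all rows of Table AMAG.6.4, as the visit or date at which permanent discontinuation of study treatment is recorded, not the last dosing visit.
2. Remove or correct the explanation in rows 3.1 and 4a.1.
3. State in SAP 6.14.2.3 that any AE recorded as the reason for stopping treatment is counted in the period in which the stop occurred.
4. Optionally, add a Period 1 sensitivity table by arm through the Period 1 end date for all subjects still in the study. Using that longer window for the main tables is not needed to cure the defect.

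The cost is SAP wording, one date rule in programming and slightly higher AE counts. No new data are needed.

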- Period 3 (Weeks 52 to 104): All subjects having clinical benefit per investigator and continuing on study treatment may proceed to Period 3 and receive 300 mg SC LY3074828 Q4W open-label starting at Week 52 through Week 104. Patients not receiving clinical benefit at Week 52 will discontinue treatment and will enter the Follow-Up period.
- Follow-Up (Weeks 104 to 120): At Week 104, subjects will stop treatment and be followed for safety for an additional 16 weeks.
- [Figure AMAG.1](#) illustrates the study design.

Abbreviations: IV = intravenous; Q4W = every 4 weeks; SC = subcutaneous; SES-CD = Simple Endoscopic Score for Crohn’s Disease.
 *Subjects who have not had any improvement in SES-CD score from baseline at Week 12, as determined by the central reader, will receive IV LY3074828 1000 mg + SC placebo.

Figure AMAG.1. Illustration of study design for Clinical Protocol I6T-MC-AMAG.

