6.1.5. Treatment Groups by Analysis Population and Analysis Period

Table AMAG.6.5 provides the treatment groups to be displayed for each analysis population and analysis period.

Table AMAG.6.5. Treatment Groups by Analysis Population and Analysis Period

Analysis Population	Analysis Period	Treatment Groups	Treatment-Group Comparison, When Applicable
ITT, mITT, Safety Population Period 1	Period 1	
 • PBO • 200 mg IV • 600 mg IV • 1000 mg IV • All LY • Total 	For ITT and mITT: 
 • 200 mg IV vs PBO • 600 mg IV vs PBO • 1000 mg IV vs PBO For Safety Population Period 1: 
 • All LY vs PBO
EHO Group 2, EHO Group 3	Periods 1, 2, 3 and f/u (where applicable)	
 • 200 mg IV/200 mg IV • 600 mg IV/600 mg IV • 1000 mg IV/1000 mg IV • LY IV/300 mg SC • 1000 mg IV for subjects showing no improvement[#] in SES-CD from baseline at Week 12 • Placebo/1000 mg IV • Total 	N/A
Safety Population Period 2	Period 2	
 • 200 mg IV/200 mg IV • 600 mg IV/600 mg IV • 1000 mg IV/1000 mg IV • LY IV/300 mg SC • 1000 mg IV for subjects showing no improvement[#] in SES-CD from baseline at Week 12 • Placebo/1000 mg IV • All LY IV • Total 	N/A
Safety population All SC LY	All treatment periods where LY SC is administered (time during either Periods 2-3)	
 • 300 mg SC * 	N/A
Safety Population All LY	All treatment periods where LY (IV or SC) is administered	
 • LY Treatment * 	N/A

Treatment Groups by Analysis Population and Analysis Period

Analysis Population	Analysis Period	Treatment Groups	Treatment-Group Comparison, When Applicable
Safety Population All LY	All treatment periods where LY (IV or SC) is administered and Follow-Up Period	
 LY Treatment and after * 	N/A

Abbreviations: EHO = efficacy and health outcomes; f/u = follow-up; ITT = intent to treat; IV = intravenous; mITT = modified intent to treat; N/A = not applicable; PBO = placebo; SC = subcutaneous; SES-CD = Simple Endoscopic Score for Crohn's Disease.

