6.14.1. Extent of Exposure

Duration of exposure to study treatment will be summarized by treatment group for Safety Population Period 1, Safety Population Period 2, Safety Population All SC LY, and Safety Population All LY. For each of the Safety Populations, exposure will be calculated as the period defined in [Table AMAG.6.4](#) plus 1 day.

Total patient-years of exposure will be reported for each of the Safety Populations by treatment (where applicable). Descriptive statistics (n, mean, SD, minimum, first quartile, median, third quartile, and maximum) will be provided for patient-days of exposure and the frequency of subjects falling into the following different exposure ranges, as appropriate, will be summarized:

- >0, ≥7 days, ≥14 days, ≥30 days, ≥60 days, ≥90 days, ≥120 days, ≥183 days, ≥365 days, ≥548 days, and ≥730 days.
- >0 to < 7 days, ≥7 to <14 days, ≥14 to <30 days, ≥30 to < 60 days, ≥60 to <90 days, ≥90 to <120 days, ≥120 to <183 days, ≥183 to <365 days, ≥365 days to <548 days, ≥548 days to <730 days, and ≥730 days.

Overall exposure will be summarized in total patient-years, derived in the following manner:

- Exposure in patient-years = Sum of duration of exposure in days (for all subjects in treatment group) / 365.25.

Additional exposure ranges may be considered if necessary.

No p-values will be reported in these tables as they are intended to describe the characteristics of the Safety Populations.

Reasons for not taking planned treatment and reasons for IV interruptions will be reviewed.

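### The All SC LY safety set closes at the last subcutaneous dosing visit and has no follow-up version, so the four weeks after a last SC dose in Period 3 enter no SC-specific safety summary

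*SAP*

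**What the plan says.** SAP 6.1.4, Table AMAG.6.4, row 3.1 opens the All SC LY window at the first SC dose of LY; the window "ends at the study treatment disposition visit (ie, the last visit at which the LY SC treatment was administered". Rows 3.2 and 3.3 (laboratory tests and vital signs) refer back to it. Row 3.3 adds: "Only scheduled visits will be included. The ETVs are considered scheduled visits". SAP 6.14.1 ties patient-years to the same table: "For each of the Safety Populations, exposure will be calculated as the period defined in" Table AMAG.6.4, plus one day.

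SAP 6.1.5, Table AMAG.6.5 gives the analysis period for All SC LY as "All treatment periods where LY SC is administered (time during either Periods 2-3", with no follow-up row. All LY has two versions. Version (b) runs to Week 120, and row 4b.1 says of it: "Note that this will include the period after discontinuing treatment". It is shown as one column that pools IV and SC.

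SAP Table AMAG.6.1 defines no safety population for Period 3. Table AMAG.6.2 ends Period 3 at the "Visit 31 dose date or the date of the ETV (if it occurs between Visits 18 and 31").

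On the protocol side, everyone who enters Period 3 receives SC treatment every 4 weeks, and the Schedule of Activities marks dosing at Visit 31 (Week 104). Protocol 5.1 then states: "At Week 104, subjects will stop treatment and be followed for safety for an additional 16 weeks".

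**The concern.** Safety and tolerability is a secondary objective, and All SC LY is the only safety set that isolates SC treatment across Periods 2 and 3. As written, it counts each subject up to the last SC dosing visit and nothing later. The consequences are:

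- Adverse events and serious adverse events that start in the 28 days after a last SC dose are not in the set.
- SAP 6.14.8.3 plans, for this population, a summary of non-immediate hypersensitivity (Time Period B), meaning events after the dosing day and before the next dose. For every subject's last SC dose that period is empty by construction.
- Period 3 assessments are done before dosing unless otherwise stated. Scheduled laboratory and vital-sign results that follow the last dose are therefore never counted, and a subject with a single SC dose has no scheduled post-dose result in the set.
- SAP 6.14.2.3 summarizes, by preferred term, subjects who "permanently discontinued from study treatment due to an AE (including AEs that led to death) during the treatment period". An event that starts between the last SC dose and the next planned one, and causes stopping, has its onset outside the window.

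The text also conflicts with itself. Row 3.3 admits early termination visits, yet one that follows the last SC dose lies outside the window. For early terminators, Table AMAG.6.2 runs Period 3 to that visit, while row 3.1 stops at their last SC dose.

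**Working it through.** **Inputs** (nominal days, protocol Schedule of Activities): V8 Day 86 (window 86–92); V17, Week 48, Day 337; V18, Week 52, Day 365 ± 5; V31, Week 104, Day 729 ± 5; V801 Day 757 ± 5; V804 Day 841 ± 5. SC interval: 28 days. Days counted = end − start + 1, matching the plus-one-day rule in SAP 6.14.1.

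**Reproducing the plan's figure.** V804 − V31 = 841 − 729 = 112 days = 16 weeks, as stated. V801 − V31 = 757 − 729 = 28 days, one dosing interval. With tolerances this is 752 − 734 = 18 to 762 − 724 = 38 days.

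**Subjects who complete Week 104.** Share uncounted = 28 / (days counted + 28).

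- SC from Week 12: 729 − 86 + 1 = 644 days; 28/672 = 4.2%. Across tolerances, 633 to 649 days are counted, giving 4.2% to 4.1%.
- SC from Week 52: 729 − 365 + 1 = 365 days; 28/393 = 7.1%. Across tolerances, 355 to 375 days are counted, giving 7.3% to 7.0%.

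**Early stoppers under the literal definition.** With k doses 28 days apart, days counted = 28(k − 1) + 1.

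- k = 1: 1 of 29 days counted, 97% uncounted.
- k = 2: 29 of 57 counted, 49% uncounted.
- k = 3: 57 of 85 counted, 33% uncounted.

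**Patient-years left out.** Per 100 SC-treated subjects, at most 100 × 28 / 365.25 = 7.7. If all 180 randomized subjects received SC (an assumed upper bound), 180 × 28 / 365.25 = 13.8.

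**SC ending in Period 2.** For SC from Week 12 to Week 48, All SC LY counts 337 − 86 + 1 = 252 of 280 days. The interval from Week 48 to Week 52 (365 − 337 = 28 days) is, however, counted for completers in the LY IV/300 mg SC group of Safety Population Period 2. That leaves Period 3 as the gap that no other SC-specific set fills.

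**The case against.** The strongest reply is that nothing is lost and little is hidden. All LY (b) keeps every event through Week 120. SAP 6.14.8.4 adds a by-subject listing of injection-site reactions. SAP 6.6 tabulates reasons for stopping study drug in Period 3, when all treatment is SC. A reader might infer that adverse events leading to discontinuation escape SC-specific display altogether. The documents do not support that: the Period 3 disposition table counts them whatever their onset date. What it lacks is preferred terms, and it does not show events that did not lead to stopping.

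A reader might also take the 97%, 49% and 33% figures as typical. They are not. A subject on SC since Week 12 has had up to ten SC doses by Week 48, so in Period 3 these figures fit only subjects who switched from IV at Week 52 and stopped soon after. They also depend on the parenthetical explanation in row 3.1. The term study treatment disposition visit is not otherwise defined; if it means the visit at which stopping is recorded, early stoppers may lose little. Early SC stoppers in Period 2 lose the interval from the Period 2 set only if the same explanation applies to row 2.1, which that row does not say.

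Nor is it right that Periods 1 and 2 always run to just before the next dose. Rows 1.1 and 2.1 take the earlier of period end and disposition visit, so that holds for completers only.

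Two further points stand. No document sets 28 days as a risk window for SC; it is simply the dosing interval. Numerator and denominator share one window, so the rates are internally consistent, and an on-treatment set is a legitimate choice. Against that, protocol 5.5 projects a trough of 3.2 µg/ml for 300 mg SC every 4 weeks, so the omitted interval is one in which drug is expected to be present. The sponsor also provided a through-follow-up set for All LY but not for SC.

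**Conclusion.** The point holds for a last SC dose in Period 3. Followed exactly, the plan leaves the next dosing interval out of every SC-specific safety summary and out of SC patient-years. The size is about 4% to 7% of person-time for Week 104 completers. It is larger for early SC stoppers only under the literal definition, and can exceed 28 days for a subject who stops SC but stays on the visit schedule. The number of events affected cannot be derived from the documents.

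This is a gap in one descriptive display. No endpoint or hypothesis test is touched, and reading it as a loss of safety data would be wrong. All LY (a), row 4a.1, has the same cut-off, but version (b) recovers those events, so it is secondary.

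The conclusion rests on the visible text. Table AMAG.6.5 carries asterisks whose footnote cannot be read in the public version, and a block before SAP 6.17 is redacted, so a further SC display there cannot be ruled out.

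**What to change.** Either of two changes closes the gap:

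1. Add an All SC LY (b) version through follow-up to Tables AMAG.6.4 and AMAG.6.5, parallel to row 4b. For Week 104 completers this adds the 112 days to V804.
2. End row 3.1 a stated interval after the last SC dose, for example one dosing interval, capped at the end of participation. For laboratory tests and vital signs, also count the first scheduled visit or early termination visit after the last dose (V801 falls 18 to 38 days after V31). For consistency, treat row 4a.1 the same way.

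In both cases, use the same end date for exposure in SAP 6.14.1. Define the study treatment disposition visit once, and reconcile it with rows 1.1, 2.1 and 3.3 and with Table AMAG.6.2.

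The cost is SAP wording, one definition and one date derivation. No new data are needed: adverse events, vital signs, chemistry and hematology are already scheduled at V801 to V804 and at early termination. The downside is that some events after dosing has stopped will be labelled treatment-emergent.
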